PROJECT DESCRIPTION

Title: Attenuation of Stress Response Using Progesterone in Individuals with Alcohol Dependence and Post-Traumatic Stress Disorder NCT02187224

1. Principal Investigator:

[name]

Authorized Prescribers: [name] MD, [name] MD, [name] MD, [name] MD

2. Purpose:

Primary Aims:

1. To test if progesterone (PROG) is more effective than placebo in reducing craving after exposure to trauma or stress cues in a laboratory paradigm among men and women with a) comorbid AUD and PTSD and b) AUD only.

We hypothesize that progesterone in comparison to placebo will significantly reduce craving for alcohol in response to trauma cues in individuals with a) comorbid AUD and PTSD and b) AUD only. Craving for alcohol will be measured using a self-report Visual Analog Scale - Craving (VASC) and the Alcohol Urge Questionnaire (AUQ).

Secondary Aims:

1. To test if progesterone attenuates stress-induced anxiety, measured by the State Trait Anxiety Inventory (STAI-6).

2: To describe PROG's subjective mood effects, we will use the Differential Emotion Scale (DES-R)

3: To describe PROG's effects on cognitive performance, we will assess the ability to inhibit incongruent competing conflicts using the Stroop Color/Word test (Stroop).

Exploratory Aims:

1. To test if progesterone is more effective than placebo in reducing drinking and relapse during one month following exposure to trauma cues *using the Timeline Follow Back Method (TLFB)*.

2. To examine if there are gender differences in progesterone effects on stress and alcohol cue-induced craving.

We hypothesize that the effects of progesterone on stress and craving will be stronger in women than in men.

3. Background:

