Results: Dually diagnosed veterans reported significantly more craving for alcohol when exposed to trauma imagery than when exposed to stressful or neutral imagery ($p<0.001$) (Figure 1). The stress response decreased with treatment, and those with high stress response on prazosin reported greater, but not statistically significant, change in their drinking at the end of treatment (Figure 2). Also, there was a significant relationship ($r=0.603$) (Figure 3) between craving and the number of drinking days at follow up.

Conclusions: The preliminary findings show that veterans with dual diagnosis report strong craving after exposure to trauma

related imagery. **Based on this result we eliminated the stress condition for the present study.** The trauma-induced response predicted drinking at the end of treatment and at follow up.

- *These finding support the notion that reactivity to stress may increase the susceptibility for relapse.*
- *This study demonstrates that we have experience with this paradigm.*
- *It validates the ability of our research team to recruit individuals with AUD and PTSD.*

4. Significance:

To our knowledge, this study is the first to examine the ability of progesterone to reduce trauma or stress-induced craving in individuals diagnosed with a) comorbid AUD and PTSD and b) AUD only. Positive findings from this study will: 1) provide evidence that progesterone is important in mediating stress and alcohol craving, 2) provide insight into the underlying mechanisms of stress and alcohol craving, 3) help identify a potential marker that will distinguish who may be at

higher risk for alcohol relapse, and 4) provide a platform for other exploratory studies that can include the use of progesterone as treatment options for AUD and PTSD.

5. Research Plan:

Participants: Participants (N=72 completers) will be eligible for the study if they fullfill the following criteria:

Inclusion criteria:

- a) men (n=36) and women (n=36) age 21 to 60;
- b) have current diagnosis of *either*:
 - 1. AUD and comorbid PTSD
 - OR
 - 2. AUD

AUD will be determined by Structured Clinical Interview for DSM-5 (SCID-5) (First, Spitzer, Gibbon, & Williams, 2015). PTSD will be determined by Clinician Administered PTSD scale (CAPS-5)(Weathers et al., 2013) and by SCID-5);

- c) drink regularly (determined by TLFB and recorded 90 days prior to the interview);
- d) are not in an active phase of alcohol withdrawal;

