- e) are not at risk for suicide; if on medication, they must be on a stable dose for at least 2 weeks;
- f) for women, have regular menses every 25-35 days.

Exclusion Criteria:

- a) current SCID diagnosis of any psychotic disorder; substance use disorder (other than alcohol, nicotine, and marijuana) in the past 30 days;
- b) current unstable medical condition; positive test results at more than one baseline appointment on urine drug screens conducted for opiates, cocaine, benzodiazepines, and barbiturates (marijuana is allowed);
- c) for women, amenorrhea, use of oral contraceptives;
- d) known allergy to progesterone or peanuts (vehicle for micronized progesterone);
- e) history of thrombophlebitis, deep vein thrombosis, pulmonary embolus, clotting or bleeding disorders, heart disease, or history of stroke.

Methods: All participants will complete 1 test day. In order to control for gender differences in progesterone levels we will test women in the follicular phase of the menstrual cycle. This experiment is a between-subject design. Before the test day every participant will receive either progesterone (200 mg. bid) or placebo in identical looking capsules for three days. In previous studies with addicted individuals, this dosing schedule of progesterone attenuated stress-induced craving and improved cognitive function(Fox et al., 2013; Sofuooglu et al., 2011). On the fourth day they will attend the laboratory session. The study will consist of four phases. 1) We will first recruit participants, obtain informed consent, and evaluate eligibility for the study. 2) Following completion of intake assessments, participants will receive a full physical examination to further determine eligibility. 3) If eligible they will be randomized to start pre-treatment with either progesterone or placebo and scheduled for the laboratory session. 4) Follow-up: Participants will be contacted approximately 1 day after completing the stress lab to see how they are doing and to answer questions about their drinking. They will also be asked to come for one follow up session 1 month later to determine their drinking habits following the lab session.

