Cardiovascular and Hormone Outcome Measures: Blood pressure and pulse will be assessed using an SD-700 monitor. To assure greater accuracy for the initial time points (baseline and time 0) four measures of blood pressure and pulse will be taken, and their average will constitute the single blood pressure and pulse measure. A single reading will be used for the other time points during testing. During the laboratory sessions we will also collect blood samples to examine the levels of allopregnanolone (ALLO) - the active metabolite of progesterone – and markers of inflammation to explore the relationship between these biomarkers and behavioral effects (urges for alcohol, anxiety, mood, cognitive functioning) of progesterone and alcohol. ECG RR intervals will be edited to remove artifact and ectopy using CardioEdit software. High and low frequency HRV will be calculated using CardioBatch software (Mind/Body Institute, U Ill Chicago).

Subject Payments: Participants will be paid \$70 for screening and diagnostic evaluation, \$80 for scripting, \$25 for each medication visit (2), \$250 for the laboratory session, and \$50 for the follow up session. Therefore, participants could earn up to \$500.

Power Analysis: Sample size estimates were determined using craving from our preliminary data. Assuming a large effect size for the within-subject comparison between progesterone and placebo ($d'=0.50$)(Cohen, 1988), $\alpha=.05$ and two-sided test, we have 80% power to detect such an effect size as statistically significant with $n=30$ subjects. Assuming 20% dropout rate we need to recruit 36 subjects in order to have complete data on 30 subjects per group.

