Method for data collection and analyses: Prior to performing statistical analyses, we will calculate descriptive statistics and will assess whether the distributions of all measures conform to normality. We will apply transformation or use nonparametric methods as necessary. We will estimate effect sizes in order to inform the design of potential future definitive studies. For the primary hypotheses we will use mixed effects models to assess change in stress reactivity after administration of progesterone vs. placebo. Study medication (progesterone and placebo), and gender will be a between subject factors, condition (trauma vs neutral) and time (pre, post and recovery following script presentation) will be used as within-subject factors. The primary stress reactivity variables will be craving. We will first compute descriptive statistics for each variable and will assess data distributions. All tests will be two-sided at 0.05 level of significance. We will use the Schwartz-Bayesian criterion (BIC) to select the best-fitting correlation structure within subject.

Study Duration: Two years.

6. References:

Allen, M. T., Boquet, A. J., Jr., & Shelley, K. S. (1991). Cluster analyses of cardiovascular responsivity to three laboratory stressors. *Psychosomatic Medicine*, 53(3), 272-288.

Blake, D. D., Weathers, F. W., Nagy, L. M., Kaloupek, D. G., Klauminzer, G., Charney, D. S., & Keane, T. M. (1990). A clinician rating scale for assessing current and lifetime PTSD: The CAPS-1. *Behavior Therapy*, 13, 187-188.

Bohn, M. J., Krahn, D. D., & Staehler, B. A. (1995). Development and initial validation of a measure of drinking urges in abstinent alcoholics. *Alcoholism, Clinical and Experimental Research*, 19(3), 600-606.

Brady, K. T., Killeen, T., Saladin, M. E., Dansky, B., & Becker, S. (1994). Comorbid Substance-Abuse and Posttraumatic-Stress-Disorder - Characteristics of Women in Treatment. *American Journal on Addictions*, 3(2), 160-164.

Breese, G. R., Chu, K., Dayas, C. V., Funk, D., Knapp, D. J., Koob, G. F., . . . Weiss, F. (2005). Stress enhancement of craving during sobriety: a risk for relapse. *Alcoholism, Clinical and Experimental Research*, 29(2), 185-195.

Bremner, J. D., Krystal, J. H., Southwick, S. M., & Charney, D. S. (1996). Noradrenergic mechanisms in stress and anxiety: II. Clinical studies. *Synapse*, 23(1), 39-51. doi: 10.1002/(SICI)1098-2396(199605)23:1<39::AID-SYN5>3.0.CO;2-1

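### The 80% power claim is for a within-subject drug comparison that this between-subject trial does not make; read as a two-arm difference of 0.50, power is about 45–55%

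*Combined protocol and SAP*

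**What the plan says.** All references are to section 5 (Research Plan) of the combined protocol and SAP unless noted.

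- **Power Analysis.** The calculation is introduced with "Assuming a large effect size for the within-subject comparison between progesterone and placebo". It takes d'=0.50 and a two-sided alpha of 0.05, and reports 80% power with n=30. It continues: "Assuming 20% dropout rate we need to recruit 36 subjects in order to have complete data on 30 subjects per group".
- **Methods.** "This experiment is a between-subject design", and "All participants will complete 1 test day". Each participant takes either progesterone or placebo for three days before that test day.
- **Method for data collection and analyses.** "Study medication (progesterone and placebo), and gender will be a between subject factors". Only script condition and time are within-subject.
- **Participants and inclusion criteria.** "Participants (N=72 completers) will be eligible for the study", made up of "men (n=36) and women (n=36) age 21 to 60".
- **Section 2, Primary Aims.** The drug effect on craving is to be tested "among men and women with a) comorbid AUD and PTSD and b) AUD only".

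**The concern.** A within-subject effect size and its paired formula apply when each person is measured under both treatments. Here nobody is, so the 80% does not describe the test of the primary hypothesis. The preliminary data do not supply such an effect either: that study gave prazosin or placebo to separate participants, and its within-subject contrasts were script type and before versus after treatment.

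The paragraph also leaves out what a reader would need to repair it. It does not say what standard deviation scales the 0.50 or which score is analysed. It does not say whether a group is a drug arm, a diagnosis or a gender. The documents also disagree on whether 72 people are to be recruited or to complete.

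This matters most if the result is null. A reader who believes the trial had 80% power would take a non-significant craving result as fair evidence against a moderate effect. On most readings of the plan it would not be.

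**Working it through.** **Inputs.** From the Power Analysis: d=0.50, two-sided alpha 0.05, n=30, 20% dropout and 36 recruited per group. From Participants: 72 in total. Assumed because the documents do not state them: 1:1 allocation and any correlation rho. Unless marked as a normal approximation, powers use the noncentral t distribution.

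**1. The plan's own figure.** For a paired comparison the normal approximation is Φ(d√n − 1.96).

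- Φ(0.50 × √30 − 1.96) = Φ(0.779) = 78%.
- The paired t-test gives 75%.
- The n needed for 80% is (1.96 + 0.84)²/0.50² = 31.4, so 32 by the normal approximation, and 34 by t.

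The stated 80% at n=30 is therefore close to a paired calculation. A two-arm calculation at 30 per arm is not close: Φ(0.50 × √(30/2) − 1.96) = Φ(−0.02) = 49%, or 48% by t.

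**2. Dropout arithmetic.** 36 × 0.8 = 28.8, not 30. Keeping 30 requires 30/0.8 = 37.5, so 38; the plan's 36 equals 30 × 1.2. For the whole trial, 72 × 0.8 = 57.6 completers if 72 is recruited, and 72/0.8 = 90 recruited if 72 is completers.

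**3. Reading A: 0.50 is the between-arm standardised difference on the analysed score, and a group is a drug arm.** The noncentrality is 0.50 × √(n/2) with 2n − 2 degrees of freedom.

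| Completers per arm | Power at 0.50 | Difference detectable at 80% |
|---|---|---|
| 28 | 45% | 0.76 |
| 29 | 46% | 0.75 |
| 30 | 48% | 0.74 |
| 36 | 55% | 0.67 |

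Reaching 80% at 0.50 needs 64 completers per arm. The dropout slip alone (30 down to 28 or 29 per arm) costs 1.3 to 2.7 points.

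**4. Reading B: as A, but the drug comparison is made within one diagnosis, as Primary Aim 1 a) and b) allow.** This also assumes an equal split between diagnoses, which the documents do not give. The same figures apply within one gender.

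| Completers per arm | Power at 0.50 | Difference detectable at 80% |
|---|---|---|
| 14 | 25% | 1.10 |
| 15 | 26% | 1.06 |
| 18 | 31% | 0.96 |

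**5. Reading C: 0.50 really is a paired effect, scaled by the SD of within-person differences.** The equivalent between-arm effect is 0.50 × √(2(1 − rho)).

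| rho | Power, 30 per arm | Power, 36 per arm |
|---|---|---|
| 0 | 77% | 84% |
| 0.3 | 61% | 70% |
| 0.5 | 48% | 55% |
| 0.7 | 31% | 37% |

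80% is reached only with 36 completers per arm and rho no higher than about 0.10.

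**6. Reading D: 0.50 is on the raw-score SD and a single change score is analysed.** The effect on the change score is 0.50/√(2(1 − rho)).

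| rho | Power, 30 per arm | Power, 36 per arm |
|---|---|---|
| 0 | 27% | 32% |
| 0.3 | 36% | 42% |
| 0.5 | 48% | 55% |
| 0.7 | 69% | 77% |

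80% requires rho of about 0.78 at 28–29 per arm, 0.77 at 30 and 0.72 at 36.

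**The case against.** Four points can fairly be made for the plan.

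**The 45–55% is one reading, not a result.** This stands. It requires 0.50 to be the between-arm difference on the analysed score and a group to be a drug arm. Across the readings above, power runs from 25% to 84%. What the documents establish is that the 80% does not belong to this design; they do not fix the true power.

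**The planned mixed model uses more data than a single change score.** This also stands, and it moves the thresholds in both directions. Assume equal correlations and a raw-score effect of 0.50. If that effect is equal at post-script and recovery, averaging the two and subtracting the pre-script score gives variance 1.5(1 − rho). At rho=0.7 the effect is 0.50/√0.45 = 0.745 and power at 30 per arm is 81%; the rho needed for 80% falls to about 0.69 (0.63 at 36 per arm). If the test is instead the trauma-minus-neutral difference in pre-to-post change, with the whole 0.50 effect in the trauma condition, the variance is 4(1 − rho). The effect is then 0.50/√1.2 = 0.456 and power is 41%. The plan names no contrast and no correlation, so it cannot rely on the favourable case.

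**That the figure came from a paired formula is an inference.** Agreed: the exact paired t-test gives 75% and needs 34. The match is suggestive only. But replacing the word within with between would not rescue the claim, since the two-arm power at 30 per arm is 48–49%.

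**The study is partly exploratory.** The analysis section does say that effect sizes will inform later definitive studies. It also tests primary hypotheses at 0.05, and the sample size is justified by the 80% claim, so that claim has to be supportable.

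**Conclusion.** The concern holds. The trial's only power statement is for a within-subject progesterone–placebo comparison, which contradicts both its design and its primary model, and nothing elsewhere in the document repairs this.

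On the direct two-arm reading with 1:1 allocation, power at 0.50 is 45–55% for 28 to 36 completers per arm, about 25 to 35 points below the claim. If the two diagnosis groups are equal in size and tested separately, it is 25–31%. Values at or above 80% need either a high within-person correlation with a favourable choice of score, or a paired effect size with 36 completers per arm and almost no correlation. The documents state none of these conditions.

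The undefined group and the conflict over whether 72 is recruited or completing are separate, real defects. The dropout arithmetic is also wrong, but its effect is small.

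**What to change.** 1. **Replace the power paragraph with a between-subject calculation.** Define group, and state the allocation ratio, the craving score and contrast analysed, the standard deviation that scales 0.50, and any assumed correlation with its source. Give power, or the detectable difference, at the number of completers expected. If 72 is the number recruited and a group is a drug arm with 1:1 allocation, suitable wording would be:

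   > With 36 participants recruited per arm and 20% dropout, about 28–29 per arm are expected to complete. This gives 80% power for a standardised between-arm difference of about 0.75–0.76, and 45–46% power for a difference of 0.50 (two-sided alpha 0.05).

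   If Primary Aim 1 a) and b) are to be tested separately, add the within-diagnosis figure and the planned split. With an equal split, about 14 per arm gives 25% power at 0.50 and a detectable difference of 1.10.

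2. **State once whether 72 is recruited or completing, and align Participants with Power Analysis.** If recruited, remove the word completers and change 30 per group to about 28–29. If completing, the per-arm completer number is 36 (55% power at 0.50, detectable difference 0.67), and 20% dropout implies recruiting 90.

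**Cost.** One rewritten paragraph, one changed phrase and a less favourable stated power. No extra participants are needed if 72 is the number recruited. If 72 means completers, recruiting 90 is what the plan's own dropout rate already implies.

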The trauma related scripts will be based on the “most traumatic” experience the participant could recall. The **stress imagery script** will be based on subjects’ description of a recent personal stressful event (e.g. breakup with significant other, a verbal argument with a significant other or family member or unemployment-related stress, such as being fired or laid off from work). Subjects will be acclimated to the procedures, warned of the risks, and trained on relaxation techniques. The neutral script will be based on previously developed neutral scripts that will consist of a relaxed beach scene commonly experienced by most individuals but personalized for each participant. Any trauma, stressful, or neutral experience related to substance use will not be considered in order to avoid eliciting internal cues related to substance use. Individual scripts will be developed using scene construction questionnaires (Rajita Sinha & Tuit, 2012). In order to maximize the differences in stress reaction between conditions among those with AUD and PTSD we eliminated the stress imagery since trauma imagery elicited stronger stress reaction when compared to neutral (see preliminary data). The questionnaires elicit details regarding the event and individuals involved, including physical sensations, thoughts, emotions, and cues related to the event described. Each scene will be audiotaped for presentation during each laboratory session. Each tape will be 5 min. long.

Relaxation Technique: Subjects will be introduced to all self-report measures and instructed how to complete them. In order to minimize baseline imagery variability participant will be given relaxation and imagery training, as described in the imagery training procedures manual (Rajita Sinha & Tuit, 2012). Relaxation training will be approximately 10 minutes and will consist of progressive muscle relaxation technique. The imagery training will consist of two types of visualizations. First, participants will be asked to visualize an unemotional scene, such as reading a magazine. Second, they will be presented with an unemotional but physically arousing scene, such as exercising in a gym. Here, the emphasis will be placed on assuring that participants are aware of physiological changes, increased heart rate, or breathing. Subjects will be given instructions throughout the imagery exercises regarding the process of imagining the scenes and maintaining the visualization for an extended period of time.

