Medication: All participants will be asked to take progesterone or placebo for three days leading up to the laboratory test day. They will be asked to take the first dose of medication

(progesterone or placebo) at night to minimize possible sedation from progesterone treatment. The following morning they will come to the clinic to take the second dose in the morning and will be given three additional doses (one to take at night the same day and two doses – morning and night for the following day). On the fourth day they will come in the morning for the laboratory session and will take one last dose in the lab. For women, the treatment will be initiated within the first 4 days of the menstrual cycle, day one being the first day of menses, and will be completed within the early follicular phase.

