There is black-box warning for progesterone regarding the risk for cardiovascular disorders and breast cancer. The black box warning mentions the Women's Health Initiative (WHI) study in which treatment of postmenopausal women (50 to 79 years of age) with daily oral conjugated estrogens combined with medroxyprogesterone acetate (MPA), relative to placebo, reported increased risks of deep vein thrombosis, pulmonary embolism, stroke, and myocardial infarction (Hammond, 2005). The pharmacological effects of MPA, a progestin, differ significantly from those of progesterone. MPA, but not progesterone, has well-characterized androgenic, glucocorticoid and anabolic effects and have been associated with unfavorable side effects including fluid retention, androgenic effects, alterations in lipid profile, increase risk for breast cancer (Fournier *et al*, 2008; Fournier *et al*, 2005), and cardiovascular events (Hermsmeyer *et al*, 2008). In contrast to MPA, progesterone is not known to cause these adverse events (Fournier *et al*, 2008; Fournier *et al*, 2005; Hermsmeyer *et al*, 2008). However, as a safety measure for these serious adverse events, we will exclude subjects with history of thrombophlebitis, deep vein thrombosis, pulmonary embolus, clotting or bleeding disorders, heart disease, or history of stroke, breast cancer or other cancers. Subjects will be

warned about these side effects and the physician will be alerted to the earliest manifestations of thrombotic disorders including thrombophlebitis, cerebrovascular disorders, pulmonary embolism, and retinal thrombosis. If any of these occur or be suspected, the study medication will be discontinued immediately. In previous studies conducted in the VA CT Healthcare System, micronized progesterone was well tolerated by both male and female cigarette smokers and cocaine users. Subjects will complete a questionnaire to note any important side-effects using the Side Effects Questionnaire (SEQ) prior to randomization (baseline), at the medication visit, and prior to the start of the laboratory session.

Progesterone effects in men: In contrast to the cyclic changes in progesterone levels in normally menstruating women, men have steady levels of plasma progesterone. The physiological levels of plasma progesterone in men are similar to the follicular phase progesterone levels found in women (Zumoff et al., 1990).

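### No craving rating is taken before study drug, so between-arm comparisons of craving level forgo a cheap baseline covariate

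*Combined protocol and SAP*

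**What the plan says.** Under Methods, medication is a between-subject factor, there is one test day, and capsules are taken for three days beforehand. The Medication section gives the count: one dose at night, one the next morning in clinic, and three to take away. Then: "On the fourth day they will come in the morning for the laboratory session and will take one last dose in the lab". That is 1 + 1 + 3 = 5 doses before the test day and a sixth during it.

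Under Laboratory sessions and Table 1, craving is rated on that day only: after set-up, before each script, after each script and after recovery.

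Before the first dose the plan schedules diagnostic interviews, the TLFB (drinking, not craving), medical assessments and script development. The Relaxation Technique paragraph says "Subjects will be introduced to all self-report measures and instructed how to complete them", but no rating is recorded there. The Progesterone section has the side-effects questionnaire completed "prior to randomization (baseline"), so self-report before randomisation already takes place.

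The primary analysis reads: "we will use mixed effects models to assess change in stress reactivity after administration of progesterone vs. placebo". Medication and gender are between-subject factors; condition and time are within-subject factors. The plan names no baseline covariate and does not say which model term tests the primary hypothesis.

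**The concern.** The analysis sentence speaks of change after administration, yet nothing is measured before administration. In the model, the earliest time level means before the script, by which point the participant has had days of progesterone or placebo. The group's own pilot, described under Preliminary Data, had a laboratory session before treatment and another during it; this trial has only the session on drug.

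Two things follow. First, if progesterone lowers resting craving, that effect is already in the pre-script rating, and a pre-to-post contrast taken alone would cancel it. Second, people differ in how much they crave. A comparison of craving level between arms carries that spread in its error term, and without a pre-drug rating none of it can be removed by adjustment. Power for a between-subject comparison is already limited at this sample size.

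**Working it through.** **Inputs.** From the documents: d = 0.50, 80% power and n = 30 (Power Analysis); two-sided 0.05 (Power Analysis and the analysis section); 72 completers (Participants), so 72/2 = 36 per arm; 30 per group (Power Analysis). Assumed: 1:1 allocation, all participants pooled, and a correlation r of 0.3 to 0.6 between a pre-drug rating and lab-day craving. The documents give neither the allocation ratio nor r.

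**1. The plan's own figure.** The Power Analysis states "Assuming a large effect size for the within-subject comparison between progesterone and placebo" and "we have 80% power to detect such an effect size as statistically significant with $n=30$ subjects". As a paired calculation by normal approximation:
- n = (1.96 + 0.84)² / 0.50² = 31.4, rounded up to 32.
- Power at n = 30 is Φ(0.50 × √30 − 1.96) = Φ(0.78) = 0.78.

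The figure is therefore close to reproduced, but only as a within-subject comparison. The mismatch with the between-subject design is a separate matter. It is used here only to set the starting point.

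**2. Between-arm level comparison without a covariate.** Two-sample noncentral t, with noncentrality d × √(n/2):
- 30 per arm: 0.50 × √15 = 1.94, power 0.48.
- 36 per arm: 0.50 × √18 = 2.12, power 0.55.
- The normal approximation gives 0.49 and 0.56, and 63 per arm for 80% power.

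**3. The same comparison adjusted for a pre-drug rating.** Residual variance is multiplied by 1 − r², so the effective d is 0.50/√(1 − r²). The equivalent gain in patients is 1/(1 − r²) − 1.

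| r | Variance cut | Equivalent extra patients | Effective d | Power, 30/arm | Power, 36/arm | Per arm for 80% (normal approx.) |
|---|---|---|---|---|---|---|
| 0 | 0% | 0% | 0.50 | 0.48 | 0.55 | 63 |
| 0.3 | 9% | 10% | 0.52 | 0.51 | 0.59 | 58 |
| 0.5 | 25% | 33% | 0.58 | 0.59 | 0.68 | 48 |
| 0.6 | 36% | 56% | 0.63 | 0.66 | 0.74 | 41 |

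**4. Reactivity contrasts.** Let B be the pre-drug rating, with all ratings at unit variance. Then corr(B, post − pre) = (r_B,post − r_B,pre) / √(2 − 2 r_pre,post), and the variance cut is its square.
- Equal correlations (compound symmetry): the numerator is zero, so the cut is 0%.
- r_B,pre = 0.6, r_B,post = 0.5, r_pre,post = 0.6: −0.1/√0.8 = −0.11, a cut of about 1%.
- r_B,pre = 0.7, r_B,post = 0.5, r_pre,post = 0.7: −0.2/√0.6 = −0.26, a cut of about 7%, the largest of the cases tried.

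**5. Simulation check.** 4,000 replicates, 30 per arm, common correlation 0.5. Variance of the estimated arm difference, without and then with B as covariate:
- Post-script level: 0.0667, then 0.0497.
- Post minus pre: 0.0646, then 0.0657.
- Trauma-minus-neutral double difference: 0.129, then 0.132.

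The covariate helps the level comparison. For the reactivity contrasts it costs only about a degree of freedom.

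**6. Resting effect.** A drug shift δ present at both pre and post contributes δ − δ = 0 to post minus pre. It remains visible in the medication effect at the pre-script time point and in the medication main effect.

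**The case against.** The strongest reply is that the primary hypothesis concerns craving in response to cues, and the model gives each participant their own reference within and across scripts. Stable differences between people then drop out of medication by time and medication by condition by time. This stands: steps 4 and 5 show almost nothing to gain there.

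Three stronger readings might be inferred, and the documents support none of them.
- *The comparison is biased or invalid without a pre-drug value.* Participants are randomised, so arms can be compared on post-treatment ratings without bias, and the standard error covers chance imbalance.
- *The plan adjusts away a drug effect on resting craving.* It does not propose subtracting the pre-script rating or using it as a covariate. It enters that rating as one level of the repeated time factor, from which a resting effect can be estimated.
- *The power gain applies to the primary test.* It does so only if that test is a level or main-effect comparison, and the plan does not say.

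The size of r is also open to challenge. Women start drug at the onset of menses, with cycles of 25 to 35 days, so a scripting-visit rating could precede the test day by weeks. A rating taken after the most traumatic memory has been elicited would not be a resting value. Either could weaken its usefulness as a covariate, and the fix has to deal with both.

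It can also be said that change after administration is just loose wording for script-induced change compared between arms. That is the only workable reading in this design, and the text should say so. It does not supply the missing covariate.

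**Conclusion.** The point holds as a cheap improvement, not as a flaw that threatens validity. No craving rating precedes study drug, so the model's first time level is pre-script only and no baseline craving covariate is available. For a post-script level or medication main effect at d = 0.50, the forgone gain is 9% to 36% of variance, or power of 0.59–0.74 instead of 0.55 at 36 per arm and 0.51–0.66 instead of 0.48 at 30 per arm. For the reactivity contrasts it is nil to about 7% of variance.

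These figures rest on r between 0.3 and 0.6, which the documents do not give and which could be lower, on 1:1 allocation, and on pooling both diagnostic groups. Aim 1 names the two groups separately. If each were tested alone with an even split, 72/4 = 18 per arm gives unadjusted power of 0.31, and all the power figures would be lower.

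The level comparison cannot be dismissed. Aim 1 refers to craving after cue exposure, which can be read as a level, and the analysis section leaves the primary term unnamed.

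**What to change.** - Record VASC and AUQ once before randomisation at an existing visit: with the baseline side-effects questionnaire, or at the scripting visit before any trauma or stress material is elicited. Place it as close to the first dose as the schedule allows.
- Enter that value as a pre-specified covariate in the primary mixed model.
- Keep the lab-day pre-script rating as a repeated outcome, as the plan already does.
- Name the model term that tests the primary hypothesis, and state that the change in question is script-induced change compared between arms. If that term is a pre-to-post contrast, also report the medication effect at the pre-script time point, so that an effect on resting craving is not lost from view.

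The cost is a few minutes of self-report, no added visit, and about one degree of freedom. The rating cannot be recovered for anyone already dosed. Improving precision on reactivity itself would probably need a pre-drug cue session like the pilot's, which is a much larger change and is not proposed here.
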